12.1.1. Baseline Data Summary

Demographic data and subjects' characteristics (e.g. vital signs) at screening will be listed and summarized using descriptive statistics. Any deviations from inclusion/exclusion criteria will be listed.

12.1.2. Responder Summary

The total number of subjects with a positive skin reaction (i.e. wheal diameter > 3mm) will be determined for the subject device and predicate device for each evaluation time point. The proportion of subjects who have a positive response to the subject device will be compared to the proportion of subjects who have a positive response to the predicate device.

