On Day 1 (Visit 1) the SPT will be performed on the infrascapular region of the back to the right of the midline. Test articles will include the subject device (KeraStat Cream), predicate devices (KeraStat Gel, Biafine), positive control (histamine), and negative control (saline). Each test article will have a single administration, only the re-test will utilize a triplicate administration. The SPT will be ready for initial reading after approximately 15 minutes (but no sooner than 10 minutes and no longer than 20 minutes) following the final SPT administration in the series. When reading the test, the investigator will note the presence or absence of a wheal at all five sites and will measure the diameter of each wheal present. In order for the SPT to be valid, the wheal at the positive control site must exceed that at the negative control by 4 mm. If the above criteria are not met, the SPT will be repeated in triplicate on the infrascapular region of the back to the left of the midline, following the same protocol. Following the initial reading, the subject will remain at the testing facility.		
A second reading will be conducted approximately 6 hours (+/- 15 minutes) after SPT administration on Day 1 (Visit 1). When reading the test, the investigator will note the presence or absence of a wheal at all five sites and will measure the diameter of each wheal present. Subjects are free to leave the clinical site after the second reading. Subjects will be instructed to promptly contact the PI and go to the ER if symptoms of an allergic reaction or shock occur.		
Subjects will return to the office one to two days after initial administration for a third test reading (Visit 2). When reading the test, the investigator will note the presence or absence of a wheal in all five sites and will measure the diameter of each wheal present.		

Study: KSCM-CRD-002	Effective Date:
Version: 01	17 Jul 19

Name of Company: KeraNetics	Name of Product: KeraStat® Cream	Type of Study: Clinical Safety
Each site of test article administration will be measured for a positive reaction. A positive reaction is present when there is a measurable wheal of 3 mm or more, surrounded by a flare. Small wheals are to be confirmed by palpation. A flare alone is disregarded.		
Inclusion Criteria: Subjects must meet all of the following criteria:		

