
Concomitant Medication Restrictions: Corticosteroids, immunosuppressive agents, radiation or chemotherapy, topical growth factors, anxiolytics, imipramine, phenothiazine, dopamine, phenergan, clonidine, montelukast, immunotherapy, UV light therapy, H-2 antagonist, cyclosporine
		

Criteria for Evaluation:
 
Skin Reaction:
 
Primary
 
 Size of wheal for the subject device and predicate device at 15 minutes post SPT administration 
Secondary
 
 Size of wheal for the subject device and predicate device at 6 hours and 1-2 days post SPT administration 
Safety Parameters:
 
 Safety of the subjects will be monitored and adverse events recorded throughout the study 		

Statistical Methods: No formal statistics will be performed to compare the subject device and predicate device. Data will be summarized for each individual subject and time point. The number of subjects that meet criteria for a positive skin reaction to KeraStat Cream and/or a positive skin reaction to the predicate device(s) will be reported.
		

Safety: All subjects who participate in the study will be included in the safety analysis. Safety will be evaluated by examining the incidence and type of adverse events from the Screening Visit through study completion.
		

Study: KSCM-CRD-002 Version: 01	Effective Date: 17 Jul 19
--	--

FIGURE 1: TIME AND EVENTS SCHEDULE

Period	Skin Prick Test	
Visits	Screening Visit / Visit 1 Day 1	Follow-Up Visit/ Visit 2 (Day 2-3)
Screening		
Informed Consent	X	
Demography	X	
Brief Medical History	X	
Inclusion/Exclusion	X	
Safety Procedures		
*Vital Signs	X	
Abbreviated Physical Examination	X	
Adverse Events	X	X
Concomitant Medications	X	X
Study Treatment/General		
Skin Prick Administration	X	
Meal	X	
Assessments		
Evaluation of Response (15 min)	X	
Evaluation of Response (6 hrs)	X	
Evaluation of Response (24-48 hrs)		X

*Vital signs include height, weight, blood pressure, pulse, temperature, and respirations per minute.

Study: KSCM-CRD-002	Effective Date:
Version: 01	17 Jul 19

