11. STUDY ENDPOINTS

11.1. Positive Reactions

During all evaluations, each site will be measured for a positive reaction. A positive reaction is present when there is a measurable wheal of 3 mm or more, surrounded by a flare. In cases where the wheal diameter is non-uniform, the longest wheal diameter should be used for the evaluation of the SPT.^{6,7} Small wheals are to be confirmed by the investigator via palpation.

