12. STATISTICS

12.1. Description of Statistical Methods

This is an observational study only; no formal statistics will be performed.

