12.3. Procedure for Accounting for Triplicate Data

In the case that a triplicate re-administration is required, wheal diameter will be averaged for each test agent. A subject will be considered to show a positive reaction to the subject device or predicate device when the average wheal diameter is greater than 3 mm.

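### A positive skin reaction is defined as 3 mm or more with flare in the synopsis and Section 11.1, but as more than 3 mm with no flare condition in Sections 12.1.2 and 12.3, and nothing says which rule governs the responder counts.

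*Combined protocol and SAP*

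**What the plan says.** The combined protocol and SAP states the rule for a positive reaction in four places.

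- **Synopsis and Section 11.1**, in the same words: "A positive reaction is present when there is a measurable wheal of 3 mm or more, surrounded by a flare". Section 11.1 gives the scope: "During all evaluations, each site will be measured for a positive reaction". The synopsis adds "A flare alone is disregarded", so flare is necessary but not sufficient.
- **Section 12.1.2**, the responder summary, counts subjects with a "positive skin reaction (i.e. wheal diameter > 3mm" at each time point, then compares the proportions for the subject and predicate devices.
- **Section 12.3**, for a triplicate re-test, averages the diameters for each agent and calls the subject positive "when the average wheal diameter is greater than 3 mm".

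Neither part of Section 12 mentions flare or refers to Section 11.1. The synopsis paragraph on statistical methods says that what is reported is "The number of subjects that meet criteria for a positive skin reaction to KeraStat Cream" or to the predicates, without saying which criteria. The reading instructions in the synopsis and Section 6.1 list two things to note at each site: whether a wheal is present, and its diameter.

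The primary endpoint is "Size of wheal for the subject device and predicate device at 15 minutes post SPT administration". On inference, Section 12.1 says: "This is an observational study only; no formal statistics will be performed".

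**The concern.** The investigator is told to judge positivity by one rule and the analyst to count it by another. The two rules differ in the cut-off (3 mm included or excluded) and in whether flare is required. Two people working correctly from the same readings could therefore report different numbers of positive subjects.

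The responder proportions are the only between-device comparison of skin results described in Section 12, and Sections 6.1 and 12.2 say the study is meant to support substantial equivalence. With no test and no threshold, the reported count carries the message. The study is also open-label, so a definition chosen after the readings are known would be hard to defend.

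**Working it through.** The plan has no derived figure to reproduce: Section 12.2 says the sample size has no statistical basis. The check is a comparison of the rules, followed by the size of one reclassification.

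**Step 1. Apply both rules to the same readings.**

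| Reading | Synopsis and 11.1 (at least 3 mm, with flare) | 12.1.2 or 12.3 (above 3 mm) |
|---|---|---|
| 4 mm, flare | positive | positive |
| 3 mm, flare | positive | **negative** |
| 4 mm, no flare | negative | **positive** |
| 3 mm, no flare | negative | negative |
| Triplicate 3, 3, 3 mm, all with flare | positive at each of the three sites | mean (3+3+3)/3 = 3.0, **negative** |
| Triplicate 2, 3, 4 mm, all with flare | positive at two of three sites | mean (2+3+4)/3 = 3.0, **negative** |
| Triplicate 3, 3, 4 mm, all with flare | positive at each of the three sites | mean 10/3 = 3.33, positive |

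Neither rule is uniformly the stricter, so the mismatch cannot be defended as conservative.

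**Step 2. Size of the cut-off gap.** The document gives no recording precision, so this is an assumed range for a single reading. The smallest recordable value above 3 mm is 3 + 1 = 4 mm at 1 mm precision, 3 + 0.5 = 3.5 mm at 0.5 mm, and 3 + 0.1 = 3.1 mm at 0.1 mm. Section 11.1 counts from 3 mm in every case.

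**Step 3. Effect of one reclassified subject.** Inputs are 20 completers and about 22 enrolled (Section 12.2). Intervals are exact (Clopper-Pearson) 95%. For 0/n the upper limit is 1 − 0.025^(1/n); for 1/n the lower limit is 1 − 0.975^(1/n).

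| n | Step, 1/n | 0 positives | 1 positive |
|---|---|---|---|
| 20 | 5.0 points | 0% (0 to 16.8%) | 5.0% (0.1 to 24.9%) |
| 22 | 4.5 points | 0% (0 to 15.4%) | 4.5% (0.1 to 22.8%) |

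The plan does not call for these intervals; they only show scale. Reclassifications in opposite directions can cancel.

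**Step 4. Chance that at least one subject is affected.** The share q of subjects reading exactly 3 mm with flare, for a given agent and time point, is not in the document. As an assumed range, with 1 − (1 − q)^20:

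| Assumed q | At least one of 20 affected |
|---|---|
| 1% | 18% |
| 2% | 33% |
| 5% | 64% |
| 10% | 88% |

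Wheals above 3 mm without flare would add to this, with no figure to base an estimate on.

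**The case against.** The strongest reply is that the governing rule can be inferred. Section 11.1 sits under the study endpoints, is titled for positive reactions and covers every evaluation. The synopsis counts subjects who satisfy criteria, and the only criteria in the synopsis are the same ones. On that reading the parenthesis in 12.1.2 is loose shorthand for the size element. This is a reasonable inference, but it does not settle the matter: 12.1.2 introduces its parenthesis as a restatement of the definition, and 12.3 writes out a subject-level rule in words with the same strict cut-off and again no flare.

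Three further points have some force.

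- **Triplicates.** Section 11.1 classifies sites, not a subject with three pricks of one agent. The 3, 3, 3 mm case therefore sets a site-level result against a subject-level one, and arises only after a failed control check. The misalignment stands, but the single-reading cases are the cleaner contradiction.
- **Flare recording.** The CRF is not in the document, and Section 16.1 requires source records to hold all pertinent observations. Flare may well be captured. What can be said is only that no section asks for it as a separate item.
- **Impact.** The primary endpoint is untouched, and the per-subject summary should let the size cut-off be re-applied later. Whichever rule is used would apply to every agent, so the comparison moves only where agents differ in reclassification. All of this limits the consequence, but the counts themselves remain ambiguous.

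**Conclusion.** The concern holds. The document gives two incompatible rules for the same reported result and no statement of precedence. The effect is confined to wheals of exactly 3 mm (or triplicate means of exactly 3.0 mm) and to wheals above 3 mm without flare. Each such subject shifts a responder proportion by 5 points with 20 completers or 4.5 points with 22, enough to turn a report of no reactions into one reaction, or the reverse. The number affected cannot be derived from the document; the precision range and the values of q above are assumptions.

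The size cut-off can be corrected after the fact from recorded diameters. The flare condition can be corrected only if flare was recorded. This should be fixed, although it does not threaten the wheal-size endpoint.

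**What to change.** Before the first reading, reconcile the synopsis and Sections 11.1, 12.1.2 and 12.3 to a single definition.

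1. The simplest alignment is the Section 11.1 wording, because the synopsis already matches it and it covers every evaluation. If the sponsor prefers the Section 12 rule, the synopsis and 11.1 must change instead.
2. With the 11.1 wording, replace the parenthesis in 12.1.2 with a reference to Section 11.1.
3. In 12.3, change the cut-off to a mean of 3 mm or more, and state how the flare condition applies across the three sites.
4. Record flare as yes/no per site at each reading, if the CRF does not already do so, and add it to the items noted in the synopsis and Section 6.1.

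The cost is wording changes and at most one yes/no item per site. Sample size, visits and the wheal-size endpoint do not change.

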12.2. Sample Size

A total of 20 subjects were deemed sufficient to assess the potential for a humoral response to KeraStat Cream compared to the predicate devices in support of establishing substantial equivalence. The sample size for the study is not based on any statistical considerations. Approximately 22 subjects will be enrolled to assure completion of at least 20 subjects.

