4. INTRODUCTION

4.1. Background

Active, healthy individuals are often involved in activities of daily living that put them at risk of sustaining acute skin trauma. Superficial to partial thickness abrasions may be the most common,¹ but other partial thickness injuries such as burns (450,000 burn injuries resulted in medical treatment in 2013)² and ulcers are also common. Due to the risk of untreated acute partial thickness wounds and burns becoming more serious chronic wounds or full-thickness burns, there is pressure on the medical community to find a cost-effective and efficacious wound dressing that supports healing.

KeraStat® Cream is a non-sterile, non-implantable wound dressing intended to act as a protective covering and provide a moist environment in the management of a variety of partial thickness dermal wounds. KeraStat® Cream is provided in a screw top tube for multiple uses. Each tube contains 1 oz (29.6 mL) of KeraStat® Cream, which contains 5% keratin protein incorporated into a cream base.

A biological safety profile has been established for KeraStat Cream. Biocompatibility studies were chosen and performed in accordance with ISO 10993-1:2007, “Biological Evaluation of Medical Devices Part 1: Evaluation and Testing.” Furthermore, KeraStat Cream has been subjected to a human subject Repeat Insult Patch Test (RIPT) to evaluate the irritation/sensitization potential of the medical device when applied to uncompromised skin. No adverse skin reactions were observed in 50 subjects evaluated in the RIPT study and KeraStat Cream was considered a non-primary irritant and non-primary sensitizer to the skin.

The current study is considered a nonsignificant risk (NSR) device study according to Food and Drug Administration (FDA) guidance and does not require an Investigational Device Exemption (IDE) in advance of study conduct. NSR device studies must follow the abbreviated requirements presented in 21 CFR 812.2(b) related to labeling, Institutional Review Board (IRB) approval, informed consent, monitoring, records, reports, and prohibition against promotion.

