6. INVESTIGATIONAL PLAN

6.1. Overall Study Design

This is a single site, within subject, open-label comparison study to assess the humoral reaction KeraStat Cream compared to predicate devices. The length of study participation for a subject is two to three days depending on when a subject returns for their final follow-up evaluation. The Acceptable Study Windows is shown in Table 2.

Sufficient subjects will be screened such that 20 total subjects will complete the study. We expect excellent retention throughout the duration of the study, so we will target recruitment of 22 subjects. The sample size for the study is not based on any statistical considerations. A total of 20 subjects were deemed sufficient to assess the potential for a humoral response to KeraStat Cream compared to the predicate devices in support of establishing substantial equivalence.

Initial screening (Screening Visit; Visit 1) of the subject will take place the day of the SPT administration. The Screening Visit will include collecting demographic information, a brief medical history, and an abbreviated physical exam. If a subject fulfills all the inclusion criteria, none of the exclusion criteria, and gives their informed consent they will be admitted into the study.

The SPT will be performed on Day 1 (Visit 1), after screening and consent is obtained. The test will include five agents: the subject device (KeraStat Cream), predicate devices (KeraStat Gel, Biafine), positive control (histamine), and negative control (saline). The SPT will be administered on the infrascapular region of the back to the right of the midline. The region will be cleaned with alcohol wipes and allowed to air dry. Five marks will be made using a sterile skin marker to identify the test sites. These marks will be at least 4 cm apart and made in a

Study: KSCM-CRD-002	Effective Date:
Version: 01	17 Jul 19

vertical line. Once the marks are made, the back will be cleaned again with alcohol wipes and allowed to air dry. All subjects will initially receive the agents in the same order, going in descending order from a subjects' head to feet: subject device, predicate device (KeraStat Gel), predicate device (Biafine), positive control, and negative control.

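### Twenty subjects are called sufficient in support of substantial equivalence with no precision target, and the positive-reaction proportions are to be compared without intervals

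*Combined protocol and SAP*

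**What the plan says.** Section 12.2 gives the size and its purpose: "A total of 20 subjects were deemed sufficient to assess the potential for a humoral response to KeraStat Cream compared to the predicate devices", and this is said to be "in support of establishing substantial equivalence". The next sentence adds: "The sample size for the study is not based on any statistical considerations". It then sets enrolment: "Approximately 22 subjects will be enrolled to assure completion of at least 20 subjects". Section 6.1 repeats the purpose ("compared to the predicate devices in support of establishing substantial equivalence") and the disclaimer, and the synopsis does the same in nearly the same words.

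On analysis, section 12.1 says: "This is an observational study only; no formal statistics will be performed". The synopsis says: "No formal statistics will be performed to compare the subject device and predicate device". Section 12.1.2 nevertheless plans to count positive reactors for Cream and predicate at each reading and to compare the two proportions. It does not say how, and it attaches no interval to either proportion or to their difference.

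Under section 6.1 a subject whose triplicate re-test also fails the control criterion is removed. Under section 7.4.3 such a subject is not replaced.

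**The concern.** The plan disclaims any statistical basis for the number 20 and also calls it sufficient for a comparison that is meant to support a regulatory conclusion. Nothing links the two statements. The documents give no reaction rate that would be acceptable, no difference from a predicate that would matter, and no confidence level.

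The practical risk lies in section 12.1.2. If few or no positive reactions occur, the report will set proportions such as 0/20 beside 0/20 with nothing to show their uncertainty. A reader can easily take matching zeros as evidence that the products behave alike. With 20 subjects, matching zeros are also compatible with a Cream reaction rate above 1 in 10.

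**Working it through.** **Inputs from the documents.** There are 20 completers and about 22 enrolled (6.1, 12.2). The design is within subject, so the same subjects supply the Cream, KeraStat Gel and Biafine results (6.1, 6.4). No alpha, power, margin, expected rate or dropout rate is given.

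**Assumptions.** The confidence level is 95%, shown one-sided and two-sided. The scenario examined is zero positive reactions; the documents do not predict it.

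**The plan's own figure.** No formula can reproduce 20, because nothing is stated behind it. The step from 20 to 22 implies an allowance of 2/22 = 9.1% for losses.

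**Step 1: Cream reaction rate after 0 of n.** The exact (Clopper-Pearson) upper limit is 1 − a^(1/n), with a = 0.05 one-sided and a = 0.025 two-sided.

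| Evaluable n | One-sided 95% | Two-sided 95% |
|---|---|---|
| 18 | 15.3% | 18.5% |
| 20 | 1 − 0.05^(1/20) = 13.9% | 1 − 0.025^(1/20) = 16.8% |
| 22 | 12.7% | 15.4% |

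As cross-checks for n = 20, the rule of three gives 3/20 = 15.0% and the two-sided Wilson limit is 16.1%. A single reaction in 20 would raise the exact upper limit to 21.6% one-sided or 24.9% two-sided.

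**Step 2: paired Cream-predicate difference.** The stated aim is comparative, so the paired limit matters as well. With no discordant pairs the score (Tango) limit is z²/(n + z²).

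- One-sided: 2.71/(20 + 2.71) = 11.9 percentage points.
- Two-sided: 3.84/(20 + 3.84) = 16.1 percentage points.

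**Step 3: chance of seeing no reaction in 20**, (1 − p)^20.

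- True rate 5%: 0.95^20 = 35.8%.
- True rate 10%: 0.90^20 = 12.2%.
- True rate 14%: 0.86^20 = 4.9%.

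**Step 4: what 'sufficient' would depend on.** With zero reactions, holding the one-sided limit at or below 10% needs ln(0.05)/ln(0.90), rounded up to 29 subjects. Holding it at or below 5% needs 59. The two-sided numbers are 36 and 72. On the one-sided limit, 20 would be enough for a 15% threshold and too few for a 10% one. These thresholds only illustrate the dependence, since the documents set none.

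**Step 5: the denominator.** Enrolling 22 absorbs two losses. Because control failures are not replaced, a third loss would take the evaluable number below 20. With 18 evaluable the limits are those in the first row of the table.

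Sections 11.1 and 12.1.2 differ on whether a wheal of exactly 3 mm is positive. That can change the count, but not the limit that goes with a given count.

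**The case against.** The strongest reply is that the plan promises no inference. It says three times that the size has no statistical basis, it rules out formal statistics, and it describes its purpose as supportive. Substantial equivalence is here a device-regulatory term, used alongside predicates and a legally marketed device, and need not mean a statistical equivalence claim. This largely stands, and it rules out several stronger readings.

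- **A reader might infer that the design cannot deliver its stated aim.** That would need a threshold that 13.9% or 16.8% fails, and the documents contain none.
- **A reader might infer that a product to which 1 in 20 people react would pass about a third of the time.** The 36% is correct as the chance of seeing no reaction, but the plan has no pass rule and does not say what follows from zero reactions.
- **A reader might take 0/20 for every product as the sponsor's expected result.** No expected rate is given for Cream, KeraStat Gel or Biafine.
- **A reader might call 0/20 weaker evidence than the earlier patch test.** Section 4.1 reports: "No adverse skin reactions were observed in 50 subjects evaluated in the RIPT study". Zero in 50 does give tighter limits (5.8% one-sided, 7.1% two-sided), but for irritation and sensitization on intact skin. Section 4.2 says the prick test is needed because that test does not address a humoral response on compromised skin.

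A further objection is that the primary endpoint is wheal size at 15 minutes, so judging 20 subjects only on a yes/no rate is incomplete. That is fair: the figures above say nothing about the precision of paired wheal sizes, and the documents give no standard deviation from which to calculate it. However, the responder proportion is the only between-product comparison that section 12 describes, so its precision should be stated.

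The disclaimer does not remove the problem. Saying that a number has no statistical basis does not tell the reader how much the resulting proportions can show. A descriptive study can report that without testing anything.

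**Conclusion.** The point holds as one about an unsupported sufficiency claim and undisclosed precision; it does not show that the design fails. Whether 20 is enough cannot be judged from the documents. With no Cream reaction in 20, rates up to 13.9% (one-sided) or 16.8% (two-sided) remain compatible with the data. With no discordant pairs, so do paired differences up to 11.9 (one-sided) or 16.1 (two-sided) percentage points.

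These figures rest on the assumed 95% level, the zero-event scenario and 20 evaluable subjects. Fewer evaluable subjects, or any reaction to Cream, would raise the limit on the Cream rate. The wording in the synopsis, 6.1 and 12.2, together with bare proportions in 12.1.2, leaves room for reading zero or few events as similarity. That is worth correcting because the correction is nearly free and bounds what the study can conclude.

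**What to change.** Keep 20 completers and make two changes.

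1. **Section 12.1.2.** Report each positive-reaction proportion with an exact 95% confidence interval, and the paired difference between Cream and each predicate with a score 95% interval, at each reading. Use the number actually evaluable and say who counts as evaluable, since section 12.4 keeps the completed assessments of withdrawn subjects in the summaries. Amend section 12.1 and the synopsis to say that no hypothesis test is performed but that these descriptive intervals are given.

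2. **Section 12.2, section 6.1 and the synopsis.** Limit the claim to descriptive support and state the precision, for example: *With 20 evaluable subjects and no Cream reaction, the exact one-sided 95% upper limit on the Cream reaction rate is 13.9%; this does not by itself establish equivalence.* A two-sided interval under change 1 would show 16.8% for the same result, so give both figures and label them.

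The cost is a less favourable stated claim and a few extra calculations. No subjects, procedures or tests are added.
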